16.5 Analyses

We will use an intention to treat approach in all our primary analyses. A per protocol analysis will be undertaken if substantial deviations from the allocated treatment or a substantial amount of missing values are observed. In all cases the per protocol analyses will serve as a "sensitivity analysis" as intended by the ICH9 guidelines and a further support for proper interpretation of the ITT conclusions.

Patients switching to steroids will be withdrawn from further data collection but are retained in the study as such. Their MAF will be included up to the time they started the new medication.

Apart from the primary analyses which focus on a specific time point (6 months), secondary analyses will take the full repeated measurements structure into account, including the 6 months values. We use a mixed model for repeated measurements with time since randomisation as a fixed covariate (or factor), lnMAF0 as a

continuous covariate and Treat as a fixed factor. We will apply an AR1 covariance structure unless the data prove this to be untenable. This model is a direct extension of the simple regression model used to test the primary hypotheses and allows estimation of treatment effect over time, including possible interactions. We will also analyze the data using generalized estimating equations (GEE), aiming to consolidate the results from the mixed model analysis.

The mixed model will take the missing values into account in a natural way, assuming of course missingness at random. A sensitivity analysis will be undertaken to verify this assumption.

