16.2 Endpoints

The primary endpoint is the mean attack frequency (MAF). Let MAF0 and MAF6 denote the MAF at baseline and the MAF at six months for a given patient. MAF0 is the baseline value for each individual patient of the primary endpoint and hence will be taken into account in the analyses as a covariate; although the primary comparison is a randomised one and MAF0 strictly speaking does not need to be taken into account, incorporating this value into the analyses will increase power and allows secondary analyses with respect to possible interaction between the treatment and the baseline level.

The MAF has a skewed distribution, and therefore we will take the (natural) logarithm in our analyses. If case MAF6 is equal to zero, we will add the minimal possible value of 0.25 (corresponding to a single attack per month) to allow taking the logarithm.

The analyses will take the general shape of a regression analysis with lnMAF6 as the dependent variable, lnMAF0 as the covariate and treatment as a fixed factor. An interaction between treatment and lnMAF0 will be added in a secondary analysis.

We assume the following model: $\ln MAF6 = a + b \ln MAF0 + c \operatorname{Treat}$, where Treat=0 for 30% stimulation and Treat=1 for 100% stimulation, thus being an indicator variable for the randomly allocated arm.

First we use an F test to evaluate (at the 5% level) the null-hypothesis

(1) H₀1: a=0 & b=1 & c=0

(effectively comparing this model to the null-model: lnMAF6=lnMAF0 in both randomised groups)

Rejection of this null-hypothesis means that we have confirmed a stimulation effect over time. Now, ONLY if (1) is rejected, do we test the following three nullhypotheses

(2a) H₀2a: a=0 & b=1 conditional on Treat=0 (30% stimulation)
(2b) H₀2b: a=0 & b=1 conditional on Treat=1 (100% stimulation)
(2c) H₀2c: c=0 (no stimulation intensity effect)

Rejection of (2c) means that we have confirmed a dose-response effect, in other words a difference between 30% and 100% stimulation.

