16.4 Power and sample size

Because of limited information about the distribution of the MAF for our specific group of patients, we conducted a small pilot study. We found a MAF of 26.42 attacks per week, with a standard deviation of 15.38. These findings did not differ very much from figures given by Burns et al. (7). These numbers correspond to lnMAF having a a mean of 3.13 and a standard deviation of 0.54.

We expect (MAF6 – MAF0) to be -9 on average in the 100% stimulation group, while we expect no reduction in the 30% stimulation group. This corresponds to (\ln MAF6 – \ln MAF0) being -0.42 on average in the 100% stimulation group.

If we assume that lnMAF0 and lnMAF6 are positively correlated, then the standard deviation of Delta = (lnMAF6-lnMAF0) would be in the range from 0.54 to $\sqrt{2}$ *0.54=0.76. Powering in terms of this Delta is a fair approximation to the regression analysis model; in fact, if the coefficient b would be equal to 1, the calculations would be identical.

Note that tests (1), (2a) and (2b) are in essence paired tests, comparing for each patient a change with respect to baseline. Test (2c) is an independent, two sample test because we compare the two treatment arms. Consequently, the test for (2c) will be the least powerful and so we performed our power analysis for that test. We did verify that all other tests are more powerful.

We attach the results of our power analysis. We conclude that if the standard deviation is 0.54 and the average of (lnMAF6-lnMAF0) is about -0.42, then 60

Protocol: Occipital nerve stimulation in medically intractable, chronic cluster headache CME Protocol number: 10.016 Version 1.11 dd. 26-09-2018 patients in each arm will allow us to detect the difference with probability 98%.

Taking a possible 20% drop-out rate into account, we propose a total study size of 144 divided equally between both arms.

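### Section 16.5 has no rule for a missing month-6 value in the primary test, and the per-protocol analysis it names for many missing values cannot reveal drop-out bias

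*Combined protocol and SAP*

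**What the plan says.** Section 16.2 defines the primary analysis at a single time point: a "regression analysis with lnMAF6 as the dependent variable, lnMAF0 as the covariate and treatment as a fixed factor". Test (2c), that the treatment coefficient is zero, is the randomised comparison of 100% with 30% stimulation.

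Section 16.4 expects losses: "Taking a possible 20% drop-out rate into account, we propose a total study size of 144 divided equally between both arms".

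Section 16.5 adopts intention to treat for the primary analyses but does not say what happens when the month-6 value is absent. Its explicit reaction is: "A per protocol analysis will be undertaken if substantial deviations from the allocated treatment or a substantial amount of missing values are observed". It calls that a sensitivity analysis. It defines neither the per-protocol set nor how much counts as substantial.

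The same section ends data collection for patients who switch to steroids, keeping their values up to the switch. It also plans secondary repeated-measures analyses that include month 6: a mixed model with arm, time and baseline, possible interactions, and GEE. The mixed model assumes missing at random, and of that assumption the plan says: "A sensitivity analysis will be undertaken to verify this assumption". No method is given.

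**The concern.** Intention to treat names who should be analysed. It does not supply an outcome for someone who has none. Without a rule, the primary regression becomes an analysis of patients with a month-6 diary.

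The stated answer to heavy missingness restricts the data further and cannot bring those patients back. If it agrees with the main result, the agreement may be read as reassurance about drop-out when it carries no information on it.

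The wording on missing at random has a related problem. Whether unseen values differ from what the seen ones predict cannot be settled from the seen ones. One can only ask how far the conclusion depends on the assumption.

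At stake is test (2c). Section 16.1 relies on it to separate a stimulation effect from a placebo effect.

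**Working it through.** **Inputs.** From section 16.4: SD 0.54 on the log scale (upper limit 0.76); mean change -0.42 at 100% stimulation; for the other arm, "we expect no reduction in the 30% stimulation group"; 20% drop-out; 144 patients, so 72 per arm. The 5% level is in section 16.2. A two-sided test is assumed for (2c), since no sidedness is stated.

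**The plan's own figure.** With 60 per arm, SE = 0.54 × √(2/60) = 0.0986 and 0.42/0.0986 = 4.26. Power = Φ(4.26 − 1.96) = 98.9%, which agrees with the stated 98%. With 20% of 144 lost, 115 remain. At 57 per arm, power is 98.6% at SD 0.54 and 83.9% at SD 0.76. At the planning SD the issue is therefore bias, not lost power.

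**Bias when loss depends on outcome in one arm.** Assumptions: no true dose effect; SD 0.54; 58 of 72 kept per arm; random loss in one arm; in the other, the patients who leave are those with the highest drop-out score, which has correlation ρ with a poor outcome. Test (1) is taken as passed.

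- Kept fraction p = 58/72 = 0.806, z = Φ⁻¹(0.806) = 0.862, φ(z) = 0.275.
- Mean shift among those kept = −ρ × SD × φ(z)/p = −ρ × 0.54 × 0.342 = −0.184ρ.
- SE = 0.54 × √(2/58) = 0.100.

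| Outcome-related loss in | ρ | Bias by formula | Simulated bias | Simulated rejection of (2c) |
|---|---|---|---|---|
| neither arm | 0 | 0 | 0.00 | 4.4% |
| 100% arm only | 0.25 | −0.046 | −0.046 | 7.8% |
| 100% arm only | 0.5 | −0.092 | −0.091 | 15.5% |
| 30% arm only | 0.5 | +0.092 | +0.092 | about 16%, by symmetry |
| both arms | 0.5 | 0 | 0.001 | 5.7% |

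Simulations used 4000 trials per setting for the first three rows and 5000 for the other biases and the last rejection rate. A bias of 0.046 to 0.091 is 11% to 22% of the planned 0.42. In the 100%-arm case it would appear as a 4.5% to 8.7% lower attack frequency (1 − e^−0.046 and 1 − e^−0.091) where there is no effect. An analysis omitting the same patients returns the same bias.

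**What the earlier months can and cannot repair.** A separate simulation assumed no effect, SD 0.54, AR1 correlation 0.8 between months, and 14 of 72 lost per arm, with outcome-related loss in the 100% arm only.

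| Loss depends on | Completer bias | Completer rejection | Bias of a missing-at-random estimator using month 5 |
|---|---|---|---|
| observed month-5 value | −0.093 | 16.6% | −0.001 |
| unseen month-6 value | −0.119 | 25.8% | −0.047 |

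Using the diary removes the first kind of bias and only part of the second. The remainder is what a missing-not-at-random analysis has to explore.

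**Tipping point under the planned result.** Suppose −0.42 is observed and 20% of the 100% arm is missing. With 57.6 per arm, SE = 0.54 × √(2/57.6) = 0.1006 and the critical difference is 1.96 × 0.1006 = 0.197. The missing patients would have to be worse than the observed ones by (0.42 − 0.197)/0.2 = 1.11 log units. At SD 0.76 the figure is (0.42 − 0.278)/0.2 = 0.71.

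**The case against.** A reader might infer that drop-out bias cannot be detected at all under this plan. Section 16.5 does not support that. The mixed model and GEE use the earlier months. A gap between the mixed model's month-6 contrast and the primary estimate would show bias explained by observed values, provided a treatment-by-time term is fitted. The plan only mentions possible interactions, and it leaves the primary test as it is. Bias from unseen values could still escape, because nothing commits the unspecified sensitivity analysis to addressing it.

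A reader might also infer that the per-protocol analysis omits exactly the same patients. That cannot be shown, since neither that set nor the primary handling of missing values is defined. What stands is that restricting the data cannot restore an outcome.

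It is tempting to expect more departures in the 100% arm because of painful stimulation. The documents do not say so: section 4 responds to pain with an extra visit at which the discomfort threshold is determined again. Loss for lack of benefit could equally fall on the 30% arm and work against 100% stimulation.

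Finally, if the planned effect is seen, the tipping points of 1.11 and 0.71 log units show a fairly robust result. That stands too. The exposure is greatest when the true effect is small or absent.

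**Conclusion.** The concern holds in limited form. The primary regression has no rule for a missing month-6 value. The reaction named for many missing values does not address them. The analyses that partly do are secondary, and the promised check is unspecified and given an aim it cannot meet.

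The illustrated error of 8% to 16% for (2c) rests on assumed one-sided, outcome-related loss. Its direction depends on the arm, and it all but disappears when both arms lose patients in the same way. Nothing in the documents says which pattern will occur. This is a correction to settle before unblinding; it does not show that the primary result will be wrong.

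**What to change.** In section 16.5:

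1. Remove missing values as a trigger for the per-protocol analysis. Keep that analysis for departures from the allocated stimulation, and define its set.
2. Run (2c) on all randomised patients, by multiple imputation of lnMAF6 from arm, lnMAF0 and the monthly lnMAF values. Alternatively, use the month-6 contrast of the planned mixed model with treatment-by-time included.
3. Pre-specify a delta-shift tipping-point analysis as the missing-not-at-random sensitivity analysis, with shifts allowed in either arm.
4. Replace the aim of verifying missing at random by assessing robustness to departures from it.

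The cost is plan wording and some programming. No new data are needed, because section 7.2 already provides a value for each 4-week period. The estimate may turn out less favourable.

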There is no established treatment for patients with MICCH. ONS has been used in open label trials with promising results (7;19-22). A prospective, randomised, controlled clinical trial is necessary to assess the efficacy, tolerability and safety of ONS in the treatment of MICCH.

4. Study design

This is a prospective, randomised, double blind, parallel group multi-centre international clinical study to compare the reduction in attack frequency from baseline of occipital nerve stimulation (ONS) in patients with MICCH between two different stimulation conditions: high (100%) and low (30%) stimulation. (see paragraph 10.1)

Active ONS is associated with paraesthesias complicating blinded comparison versus no stimulation. From our own experience with patients treated with ONS, we know that patients might find it difficult to differentiate paraesthesias associated with 100% and 30% stimulation. Recognition of the stimulation intensity would be further complicated by stepwise increasing the stimulation intensity.

Patients will be included for a 3 month baseline period, of which the first month serves for practice only. If the patient still meets the inclusion criteria after this baseline period, he/she will be randomised and scheduled for surgery. Following surgical implantation there will first be a run-in phase of 10 days of 10% stimulation intensity until wound check, followed by a stepwise increase up to either 30% or 100%. Patients in the 100% stimulation arm will receive this intensity for 4 months.

Patients will be assessed every month by the blinded study neurologist. If the patient finds the stimulation painful in between follow-up moments, an extra follow-up moment will be arranged soon and the threshold for discomfort will be defined again. The primary outcome measure is the number of attacks over the last 4 weeks of the double blind 6 month treatment period. Hereafter, in an open extension phase of 6 months, all patients will receive 100% stimulation or the stimulation considered optimal by the patient. The patients will fill in an (electronic) diary during the whole study period.

Rationale design

We estimated the effect of ONS in three Dutch patients. We found that sensation threshold and discomfort threshold can be repeatedly defined and that patients could not distinguish small differences in stimulation.

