7.1 Primary

The primary endpoint is the mean attack frequency (MAF) over the last 4 weeks in the 100% and the 30% treatment groups at 6 months.

An attack is defined as any attack recognised by the patient as being a CH attack. So also the attacks treated with oxygen or triptans.

(For consistency of calculation, any reference in this document to a month shall mean a period of 4 weeks.)

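### Section 16.5 promises intention to treat but stops data collection at steroid start, so patients who start before the last 4 weeks of month 6 have no MAF6 for the primary regression

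*Combined protocol and SAP*

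**What the plan says.** Section 16.5 sets the principle: "We will use an intention to treat approach in all our primary analyses". Two sentences in the same section deal with steroid starts: "Patients switching to steroids will be withdrawn from further data collection but are retained in the study as such", and "Their MAF will be included up to the time they started the new medication".

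The primary endpoint in Section 7.1 is the "mean attack frequency (MAF) over the last 4 weeks in the 100% and the 30% treatment groups at 6 months". Section 16.2 analyses it by "regression analysis with lnMAF6 as the dependent variable, lnMAF0 as the covariate and treatment as a fixed factor", so each patient must supply one MAF6.

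The mixed model in Section 16.5 uses all repeated measurements under missing at random, but it is a secondary analysis. The promise that "A sensitivity analysis will be undertaken to verify this assumption" belongs to that model. A further sentence reads: "A per protocol analysis will be undertaken if substantial deviations from the allocated treatment or a substantial amount of missing values are observed". The plan treats that per-protocol analysis as a sensitivity analysis.

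Under Section 8.1, patients agree not to start new prophylaxis, including steroids, from 4 weeks before baseline to the end of the double-blind phase. That section also describes corticosteroids as often efficacious, limits their use to 6-8 weeks, and does not require patients to be intractable to them.

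**The concern.** A steroid start is foreseeable and probably related to outcome, because patients who are doing badly have most reason to start. At that moment the plan stops recording the outcome. A start before the last 4 weeks of month 6 leaves no MAF6. A start within those weeks leaves part of a window, and nothing says whether that part counts. Starts after month 6 do not touch the primary endpoint.

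An ITT analysis includes every randomised patient's outcome. Here the rule makes that impossible for an unknown number of patients, and the lost diary days cannot be recovered. Some of the lost data would be free of concurrent steroid use. With 4-week months, the primary window is weeks 21 to 24, and an 8-week course begun at the end of week 12 ends at week 12 + 8 = 20.

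The economic evaluation is affected too. Section 11.3 declares an ITT analysis with data from all participants. Its attack counts and monthly SF-36 come from the same diary (Sections 9.6 and 11.2), so both are lost for these patients. Most cost data come from telephone interviews and depend less on the diary.

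**Working it through.** **1. What each analysis can use from a patient who starts steroids before week 21.**

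| Analysis | Status in plan | Can it use this patient? |
|---|---|---|
| Regression of lnMAF6 | Primary, ITT | No, MAF6 is not observed |
| Mixed model / GEE | Secondary | Yes, pre-steroid months only |
| Missing-at-random check | Attached to the mixed model | Does not supply MAF6 |
| Per protocol | Sensitivity | Does not supply MAF6 |

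The instruction to include MAF up to the steroid start suits the repeated-measures model. It does not define MAF6.

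**2. The plan's own figures (Section 16.4).** A MAF of 26.42 with SD 15.38 gives a log-scale SD of sqrt(ln(1 + 15.38²/26.42²)) = 0.54 and a mean of ln 26.42 - 0.54²/2 = 3.13. A fall of 9 gives ln(17.42/26.42) = -0.42. With 60 per arm, 0.42/(0.54 × sqrt(2/60)) = 4.26, and two-sided 5% power is Φ(4.26 - 1.96) = 0.989. This reproduces the stated 98% closely.

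**3. Assumptions for the size of the effect.** From the plan: 72 per arm (144/2), lnMAF mean 3.13 and SD 0.54, c = -0.42 or 0. Assumed: baseline to month-6 correlation 0.5, which makes the SD of change sqrt(2 × 0.5) × 0.54 = 0.54, the lower end of the plan's range. Also assumed: steroid starts of 5, 10 or 20% in the 30% arm, more likely with a poor outcome (logistic, slope 1 or 2 per SD, on level or on change). Starts followed either the month-6 value (8,000 simulated trials per setting) or earlier monthly values (3,000 trials).

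**4. Same mechanism in both arms, starters dropped.**

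| Start rate, 30% arm | Complete-case c (true -0.42) |
|---|---|
| 5% | -0.42 to -0.40 |
| 10% | -0.41 to -0.38 |
| 20% | -0.41 to -0.36 |

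At 20% in the 30% arm, the same mechanism gives about 8-11% in the 100% arm, because fewer patients there do badly. Direct check of the worst value: residual SD = 0.54 × sqrt(1 - 0.5²) = 0.468. With 20% and 10% missing, 57.6 and 64.8 patients remain, so SE = 0.468 × sqrt(1/57.6 + 1/64.8) = 0.085. Power is Φ(0.36/0.085 - 1.96), about 0.99. With c = 0, rates are equal in expectation and type I error stays at about 5%.

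**5. True c = 0 with unequal rates.** Complete-case c is biased by +0.02 to +0.08, against the 100% arm.

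| Rates (30% v 100% arm) | Starts follow month-6 value | Starts follow earlier diaries |
|---|---|---|
| 20% v 10% | 7-10% reject | 5-6% reject |
| 20% v 5% | 10-17% reject | 6-8% reject |

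Direct check at 20% v 5%: SE = 0.468 × sqrt(1/57.6 + 1/68.4) = 0.084. A bias of 0.02, 0.04 or 0.08 then gives Φ(-1.96 + bias/SE) + Φ(-1.96 - bias/SE) = 6%, 8% or 16%.

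**6. If diaries continue.** With no residual steroid effect in the last 4 weeks, c is unbiased and type I error is 5%. Suppose instead that steroids still cut attacks by an assumed 30% or 50%, that is, by 0.357 or 0.693 on the log scale. The shift in c is the difference in start rates times that amount. At 20% v 5% it is 0.15 × 0.357 = +0.05 or 0.15 × 0.693 = +0.10. With c = 0, simulated rejection is then 10-12% or 22-30%, and at 20% v 10% it is 7-8% or 13-16%. Under the planned effect at 20% switching, c is about -0.39 to -0.335. The mixed model on pre-steroid months gave about -0.42 and 0.00 in the monthly scenarios. There, starts depended on recorded values, so missing at random held by construction.

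**The case against.** The strongest reply is that censoring at a prohibited treatment is a legitimate choice. Starters keep their randomised arm, and the 20% drop-out allowance suggests that patients without MAF6 simply do not contribute. On that view complete-case is the natural default, and the planned mixed model already covers the rest. This largely stands as to size: with one mechanism in both arms the damage is small. It does not stand as to the text. An analysis that drops these patients is not the declared ITT analysis, and no sentence says that they are dropped.

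It is also fair that continued collection can do worse than complete-case as an estimate of the steroid-free effect when the residual steroid effect is large and rates differ. That is a real cost of the fix.

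A reader might infer several stronger points that the documents do not support.

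- **A contradiction with the diary schedule.** Section 4 says "The patients will fill in an (electronic) diary during the whole study period", and Section 9.6 has all patients return at 6 and 12 months. These are general schedules, to which Section 16.5 reads as a specific exception.
- **General inflation of type I error.** With c = 0, outcome-driven switching gives equal expected rates. Unequal rates need an arm-specific cause, such as unblinding, and none is stated.
- **A free choice between dropping patients and carrying values forward.** Carry-forward is named nowhere. If the favourable result were picked afterwards, test (2c) would be significant under at least one reading in 6-8% of trials with equal rates, 8-11% at 20% v 10% and 9-14% at 20% v 5%. These figures are only an upper bound.

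**Conclusion.** The point holds in limited form and should be corrected. Section 16.5 declares ITT and, by a stated rule, removes the outcome that the primary regression needs for anyone who starts steroids before the last 4 weeks of month 6. It gives no rule for a start within those weeks. The economic ITT analysis loses diary outcomes for the same patients.

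The likely size is modest: attenuation of c by at most about 0.06 (-0.36 against -0.42) at up to 20% switching by a common mechanism, with little loss of power and no inflation of type I error. Larger error rates, roughly 6-17% at 20% v 5%, require unequal rates under no true effect. All of this rests on assumed switch rates, a correlation of 0.5 and the plan's lower SD of 0.54. The gap in the text does not depend on any of these. The documents do not support a claim that the trial is underpowered or its primary test invalid for this reason.

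**What to change.** Replace the two steroid sentences in Section 16.5 with wording to this effect: patients who start steroids continue the electronic diary through months 6 and 12; steroid start and stop dates are recorded; every observed MAF6 enters the ITT primary regression.

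In addition:

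- Before unblinding, fix one MAF6 rule for partial last windows and for diaries already stopped.
- Report the planned mixed model on pre-steroid data, with a treatment-by-month term, beside the primary result as the steroid-free sensitivity analysis.
- Report the number and timing of steroid starts per arm.

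The cost is wording and two date fields, since the diary already exists. Section 15.3 requires ethics approval before the amendment takes effect, in each participating country. The ITT estimate will include any steroid effect still present in the last 4 weeks. That pulls c towards zero under the planned effect. If start rates differ, it biases c against the 100% arm as an estimate of the steroid-free effect, possibly by more than complete-case does. The report should say so. No change to treatment is proposed.

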7.2 Secondary

MAF: We will repeat the primary analysis, with the MAF as outcome instead of the logarithm of the MAF.

MAF during follow-up: The MAF for each 4 week period of the whole follow-up period.

Mean attack intensity: The mean attack intensity (on a scale from 0-10) will be calculated over the last 4 weeks for each group at baseline, 6 and 12 months follow up and will be compared between and within the 2 groups.

Responder rate: Rate of responders (>50% reduction in attack frequency in the last 4 weeks compared to baseline) will be calculated and compared between groups at 6 and 12 months.

Economic evaluation: see paragraph 11.

Anticipated group randomisation: The patient and assessors will be asked at 6 months follow-up (before deblinding), in which treatment group (high or low stimulation) they think the patient was allocated.

Awareness of paraesthesias: localisation and strength will also be evaluated weekly and coded through the patients' recordings in the electronic diary and compared with effectiveness of stimulation, e.g. frequency of attacks.

Picture used to code location of stimulation.

From: Stimulation Ranges, Usage Ranges, and Paresthesia Mapping During Occipital Nerve Stimulation

Trentman T.L. et al., Neuromodulation, 2008 (26)

The use of acute attack medication: The number of doses of sumatriptan injections or intranasal spray or O_2 inhalation periods will be investigated and calculated of the last 4 weeks of each treatment period and the baseline period, and compared between and within groups.

Patient satisfaction: We will ask the patient at 6 and 12 months follow-up whether he/she would recommend the treatment to another patient using a 5 point (Likert) scale: Strongly disagree, disagree, neither agree nor disagree, agree, strongly agree.

Responder identification: It is also investigated whether predictive factors can be identified with respect to the outcome in a hypothesis generating manner. We will look at the body mass index (BMI) and assess the predictive value of response after 5-7 days.

Adverse events: All and treatment-related adverse events will be documented by the investigators.

8. Patient Selection Criteria

Diagnosis of patients with CH shall be in accordance with *The International Classification of Headache Disorders, 2nd Edition: (1)*

A. At least 5 attacks fulfilling criteria B–D

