9.6 Surgery and hospital visits

The period of surgery and defining and adjusting the stimulation parameters will take approximately 2-3 days. After 10 days, the patient returns to the hospital for examination of the wound and removing stitches and test the system (impedances), and calibration of stimulation. After month 1, 2, 4 and 6 the patient will return to the clinic for evaluation and stimulation adjustments. The study neurologist will be seeing the patient on a monthly basis during the blinded part of the study(with the exceptions of visits 3 and 5 months follow-up which can be replaced by telephone calls in case the patient prefers this); this will be on a 3-monthly basis during the second part. During these evaluations the following scores will be taken (in the electronic diary or during an interview): *for details see appendix 24.1*

Protocol: Occipital nerve stimulation in medically intractable, chronic cluster headache CME Protocol number: 10.016 Version 1.11 dd. 26-09-2018 Electronic diary in Promise:

- Medication use
- Frequency of attacks of CH and other headache attacks
- Intensity of attacks: Numeric pain rating scale (only during the 6th and 12th month and 2 weeks before for practice)
- Absenteeism from work
- The awareness of paraesthesias: localisation (coding system) and strength (0= no paraesthesias 10= strongest paraesthesias
- Monthly SF-36

Interview:

- Adverse events; painful stimulation, neck stiffness, uncomfortable feeling of the device, infection, lost sensation of stimulation, when suspected lead migration: X-ray cervical spine
- Patient satisfaction

Before evaluations patients fill in their daily electronic diary, which will be send to our database after every 7 days (the patients will get a reminder per email or telephone). In the case of holiday, or not possessing a computer with internet access or another reason that discourages the patients from filling in the electronic diary, the patient receives a hard copy form of the diary, which can be copied to the electronic diary later.

At 6 and 12 months post randomisation, all patients return to the study neurologist/ study coordinator for the final recording of the headache diary and interview. The patient will be asked at 6 and 12 months follow-up to which group they think they have been randomised in the first 6 months treatment period and if he/she would recommend the treatment to other patients.

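### The secondary mixed model is timed from randomisation and does not pre-specify a treatment-by-time term, so its Treat coefficient, as listed, is a diluted time average and not the month-6 dose effect

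*Combined protocol and SAP*

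**What the plan says.** **The model.** Section 16.5 describes the secondary analysis thus: "We use a mixed model for repeated measurements with time since randomisation as a fixed covariate (or factor"), with lnMAF0 as a "continuous covariate and Treat as a fixed factor". The covariance is AR1 unless the data rule it out. The section presents the model as a straightforward generalisation of the primary regression and adds that it "allows estimation of treatment effect over time, including possible interactions". A GEE analysis of the same data is planned alongside. On missing data, the model is said to rely on missingness at random, and "A sensitivity analysis will be undertaken to verify this assumption".

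**The outcome.** Section 7.2 lists as a secondary endpoint "The MAF for each 4 week period of the whole follow-up period".

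**The treatment course.** Under Section 4, a patient who still qualifies after baseline "he/she will be randomised and scheduled for surgery". After implantation both arms run at 10% for 10 days and are then stepped up. "Patients in the 100% stimulation arm will receive this intensity for 4 months", that is, four of the six blinded months. Section 9.2 places the last scheduled change of stimulation at month 2. In the six-month open phase every patient receives 100% or the level he or she considers optimal.

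**The visit clock.** The follow-up table in Section 4 counts visits from surgery. Section 9.6 says: "At 6 and 12 months post randomisation, all patients return to the study neurologist".

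**The concern.** The difference between the arms is not constant over follow-up. It is absent before surgery and during the 10% run-in, grows during titration, is complete for about four months, and is no longer enforced after month 6. A Treat term without a Treat-by-time term summarises all of this in one weighted average. Counting time from randomisation adds any pre-implant weeks to that average and puts patients at different titration steps into the same nominal month.

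The primary regression in Section 16.2 estimates the difference at month 6. The mixed model as listed estimates something else, so it does not extend that regression in the sense the plan intends. This matters because Section 16.5 gives no rule for a missing month-6 value in the primary regression, while Section 16.4 allows for 20% drop-out. The mixed model and its companion GEE are where patients with partial follow-up contribute. A diluted estimate there could seem to contradict a month-6 result with which it is in fact compatible.

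Four choices also stay open until the data are seen: time as covariate or factor, interaction in or out, blinded periods only or all periods, and which contrast is reported.

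A smaller, separate point: missingness at random cannot be verified from observed data, so the sensitivity analysis cannot do what it is said to do.

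**Working it through.** **1. The plan's own figure.** Section 16.4 gives 98% power for the month-6 comparison with 60 per arm, a difference of 0.42 and SD 0.54. Standard error = 0.54 x sqrt(2/60) = 0.0986; 0.42/0.0986 = 4.26; power = Phi(4.26 - 1.96) = 98.9% (98.8% with the t distribution; two-sided 5% assumed). The figure reproduces. It belongs to the primary test, which does not use the mixed model.

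**2. What a common Treat term estimates.** With complete data, the coefficient is the weighted mean of the period-specific differences, with weights proportional to Sigma^-1 1. Under AR1 with correlation r, the first and last periods have weight 1 and each interior period has weight 1 - r.

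**3. Assumed profile.** Section 10.1 names 10, 20, 40 and 70% levels but does not assign them to arms or months. I assume 40 v 20 in the first step, 70 v 30 in the second, then 100 v 30, with effect proportional to the gap.
- Second period: 40/70 = 0.57 of the full effect.
- First period: 20/70 = 0.29 before allowing for the 10-day run-in at 10% in both arms; I use 0.17.
- Periods 3 to 6: 1.

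**4. Six blinded periods timed from surgery.**
- Equal weights: (0.17 + 0.57 + 4)/6 = 0.79.
- r = 0.5: (0.17 + 0.5 x 3.57 + 1)/4 = 0.74.
- r = 0.8: (0.17 + 0.2 x 3.57 + 1)/2.8 = 0.67.

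On the planned 0.42 this is 0.28 to 0.33. A Treat x period model with the contrast at month 6 returns the full 0.42.

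**5. Sensitivity to the titration assumption (r from 0.3 to 0.9).**
- 20/70 and 40/70, no allowance for the run-in: 68-79%.
- No effect in the two titration months: 54-65%.
- Full effect from the first month: 100%, no loss.

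**6. A wait between randomisation and surgery.** The documents give no interval; these waits are hypothetical. The profile of step 3 is shifted and the first six periods since randomisation are averaged (equal weights, r = 0.5, r = 0.8).
- Four weeks: 3.74/6 = 62%; (0.5 x 2.74 + 1)/4 = 59%; (0.2 x 2.74 + 1)/2.8 = 55%.
- Eight weeks: 2.74/6 = 46%; (0.5 x 1.74 + 1)/4 = 47%; (0.2 x 1.74 + 1)/2.8 = 48%.

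**7. If the open phase were included (12 periods timed from surgery).**
- No difference between arms after month 6: 4.74/12 = 40%; (0.17 + 0.5 x 4.57)/7 = 35%; (0.17 + 0.2 x 4.57)/4 = 27%.
- Half the difference persisting: (4.74 + 3)/12 = 65%; (0.17 + 0.5 x 7.07 + 0.5)/7 = 60%; (0.17 + 0.2 x 7.07 + 0.5)/4 = 52%.

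**The case against.** The strongest reply is that Section 16.5 never commits to one common effect. A reader might infer a single coefficient for the whole of follow-up, but the section expressly allows treatment effects over time and interactions. That stands: the fair criticism is that the interaction and the month-6 contrast are not pre-specified. Allowing an interaction also leaves the time origin unchanged.

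Other inferences go further than the documents support.
- *A long wait before surgery.* Section 9.1 mentions waiting lists as the reason for planning surgery in advance, and its two months of scheduling appear to overlap the baseline diary. The interval is unfixed, not known to be long, and the reference to randomisation in Section 9.6 may be loose wording for visits counted from surgery.
- *Open-phase data in the model.* Section 7.2 makes this plausible, but Section 16.5 does not say it.
- *Both arms at 100% after month 6.* The plan also allows the level the patient finds optimal, so a difference may persist.
- *The only analysis using partial follow-up.* The planned GEE uses the same data.
- *A faulty covariance choice.* Nothing here shows AR1 to be wrong, and the plan already allows departure from it.

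Finally, the analysis is secondary. The dose effect is tested through H02c in Section 16.2, which does not use this model.

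**Conclusion.** The point holds for a secondary analysis. Section 16.5 sets the clock at randomisation and lists no Treat-by-time term, for a contrast that starts after surgery, builds over about two months and is released after month 6. As listed, the Treat coefficient is a diluted time average.

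The illustrative size is 67-79% of the month-6 effect over six blinded periods timed from surgery, resting on an inferred titration schedule, a proportional response and AR1 correlation up to 0.8. The loss is zero if the effect is full at once, and larger with a surgical delay or open-phase data. None of these quantities is given in the documents, so the direction is firmer than the number.

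A reader might infer that the primary conclusion is at risk or that one arm is favoured. Neither follows: the month-6 test, its alpha and its power are untouched, and nothing in the documents ties the wait for surgery to the arm. The change should be made, but the trial's main result does not depend on it.

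**What to change.** In Section 16.5:
- Define period as the 4-week period since surgery, as a factor.
- State how randomised but never-implanted patients are handled, since they have no surgery date; the planned surgery date is one option for their time zero.
- Pre-specify Treat x period, fit the blinded periods only, and report the month-6 contrast.
- Apply the same specification to the GEE.
- Analyse months 7-12 separately.
- Keep the AR1 rule, or relax it as the plan already allows.

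Reconcile the clock in Section 9.6 with the follow-up table in Section 4.

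Minor: replace the aim of verifying missingness at random with a delta-adjusted sensitivity analysis of the month-6 contrast, showing how far the conclusion depends on that assumption.

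The cost is wording, with the same data and software. The model gains a few parameters, and the month-6 contrast is slightly less precise than a pooled Treat effect.
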